## 11. MANAGEMENT AND REPORTING OF ADVERSE EVENTS/ADVERSE REACTIONS

### 11.1. Single reference document in safety of use

The Summary of Product Characteristics (SmPC) in force in France will be the unique reference document on safety in this study. It will be used by the Pfizer pharmacovigilance department to evaluate all events concerning safety of use reported to the Pfizer pharmacovigilance department by the participating doctor during the study.

This unique reference document on safety must be used by the participating doctor for prescribing information and recommendations.

### 11.2. Requirement in terms of pharmacovigilance

Table 5 in the following summarizes the requirements for recording of adverse events in the electronic case report forms and for reporting adverse events via the adverse event report form of non-interventional studies to Pfizer pharmacovigilance (NIS AEM Report Form). These requirements are defined for three types of events: (1) serious adverse events (SAE), (2) non-serious adverse events (AE) (if applicable), and (3) situations involving exposure to a medicinal product including exposure in pregnancy, exposure during lactation, medicinal product errors, overdose, misuse, extravasation, lack of efficacy and occupational exposure. These events are defined in the section entitled “Definition of an adverse event”.

**Table 5: Requirements for recording of adverse events**

Adverse event	Recorded in the electronic CRF of the study	Reported via NIS AEM Report Form to Pfizer Pharmacovigilance within 24hr following awareness of the event
---------------	---	---

Adverse event	Recorded in the electronic CRF of the study	Reported via NIS AEM Report Form to Pfizer Pharmacovigilance within 24hr following awareness of the event
SAE	All	All
Non-serious AE	All	All
Situations involving exposure to a study medicinal product including exposure in pregnancy, exposure during lactation, medicinal product errors, overdose, misuse, extravasation; lack of efficacy and occupational exposure	All (independently of presence of a concomitant AE) except for occupational exposure	All (independently of presence of an associated AE)  Note: Any associated AE is reported together with the exposure scenario.

For each AE, the participating doctor must look for and obtain sufficient information both to determine the outcome of the adverse event and to evaluate if it satisfies criteria for classification of an SAE (see section entitled “Serious adverse event” in the following).

Adverse events must be reported to Pfizer within 24 hours following awareness of the event by the participating doctor, **whether the event has been considered as related to the study medicinal product or not by the participating doctor.**

In particular, if a serious adverse event is fatal or life-threatening, its reporting to Pfizer must be done immediately, whatever the information available on the adverse event. This time period also applies to all new information (follow-up) relating to reports of previously transmitted adverse events. In rare cases where the participating doctor is not immediately informed of occurrence of an adverse event, the participating doctor must report the event within 24 hours after he/she has become aware of it and report the time when he/she became aware of this adverse event for the first time.

For adverse events considered as serious or identified in the right column of the aforementioned table which are to be reported to Pfizer within 24 hours following awareness of it, the participating doctor is required to look for and to provide all additional information to Pfizer in conformity with this time period of 24hr. Furthermore, Pfizer can request from a participating doctor to obtain urgently information on specific additional follow-up. This information can be more detailed than that recorded in the study case report forms. Generally, such information will include a description of the adverse event in a sufficiently detailed manner to enable medical evaluation of the case, and independent determination of possible causal relation. All relevant information concerning the event, such as concomitant

treatments or disorders, must be provided. In the event of death of a patient, a summary of results of an autopsy available must be sent as soon as possible to Pfizer or to its certified representative.

### **11.3. Period of reporting**

For each patient, the period of reporting of adverse events starts from the time when the patient received the first dose of the study medicinal product or starting from the date on which the patient provided his/her informed consent if he/she has already been exposed to the study medicinal product, and ends at the end of the observation period of the study, i.e. at least at the end of a period of 28 calendar days after the last administration of the study medicinal product (bosutinib); a report must be sent to the PFIZER Pharmacovigilance department or its certified representative for all types of adverse events listed in the abovementioned table and which occurred during this period. If the patient received the study medicinal product on the last day of the observational period, the period of reporting will be extended by 28 calendar days after the end of the observation period. Most often, the date of signature of the consent form corresponds to the date of inclusion of the patient in the study.

In some cases, there may be a difference between the date of signature of the consent form and date of inclusion in the study.

In the event that the patient provided his/her consent but was never included in the study (for example, a patient changed his / her mind on participation; screening failure), the period of reporting ends on the date of decision of non-inclusion of patient.

If the participating doctor becomes aware of a SAE that occurred at any time after the end of the observational period and that is considered related to the study medicinal product (bosutinib), this SAE must also be reported to the Pfizer Pharmacovigilance department.

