### 9.2.1. Criteria for inclusion

Patients must satisfy all of the following criteria for inclusion in order to be eligible.

- Male or female patient 18 years of age or older;
- Patient with BCR-ABL Philadelphia chromosome positive or negative CML, in chronic, accelerated or blast phase;
- Patient resistant or intolerant to previous therapy with TKI for CP, AP or CB CML other than bosutinib;
- Patient initiating treatment with bosutinib for treatment of CP, AP or BP phase Ph+ / - CML at the end of the inclusion visit or during the one month prior to it;
- Patient who has been informed that a method of contraception must be used if a risk of pregnancy exists.
- Patients who have been informed about the study and who signed the informed consent form.

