### 9.3. Variables

Patients will be identified indirectly via a unique number in the study (the centre no., patient no. pair).

The following “patient” data will be collected in the setting of the study at the usual consultation of patients in the centres.

Data	Role	Source
Compliance with criteria for inclusion and non-inclusion	Baseline characteristics	Inclusion visit
Demographic characteristics (year of birth, gender, weight, height, ECOG performance status)	Baseline characteristics	Inclusion visit
Diagnosis of CML (date of diagnosis, phase of CML at time of diagnosis, tests performed for diagnosis)	Baseline characteristics	Inclusion visit
Transcription of BCR-ABL gene at time of diagnosis	Baseline characteristics	Inclusion visit
Previous treatments of CML (type, dose, dosage, duration of previous treatment)	Baseline characteristics	Inclusion visit
Best response to previous treatments	Baseline characteristics	Inclusion visit
Reasons for change of previous treatments (if discontinuation for toxicity, description of the AE: type and grade)	Baseline characteristics	Inclusion visit
Phase of CML in the estimate of the participating doctor, at time of initiation of treatment with bosutinib	Baseline characteristics	Inclusion visit Follow-up visit
Evolution of mutational profile of BCR-ABL gene at time of initiation of treatment with bosutinib	Baseline characteristics	Inclusion visit Follow-up visit
Concomitant treatments at time of inclusion in the setting of management of CML	Baseline characteristics	Inclusion visit
Biological and hematological assessment data	Baseline characteristics Evaluation end point	Inclusion visit Follow-up visit
Hematological, cytogenetic and molecular response at time of inclusion and results	Baseline characteristics	Inclusion visit
Description of initiation of treatment with bosutinib (date of initiation, dose, dosage)	Baseline characteristics	Inclusion visit
Change to concomitant treatments in the setting of management of CML	Evaluation end point	Inclusion visit Follow-up visit
Description of treatment with bosutinib (changes to dose or dosage, temporary or permanent discontinuations of treatment)	Evaluation end point	Follow-up visit
Safety in treatment with bosutinib	Evaluation end point	Follow-up visit
Management of toxicities related to bosutinib (concomitant treatments, additional corrective medical measures)	Evaluation end point	Follow-up visit

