#### **9.6.1.1. Channel of CRF and data entry**

Data collected by the participating doctor at time of inclusion and in the follow-up of patient visits will be recorded directly in the eCRF of the study.

For each centre, a registry will be made available to investigators to list patients eligible but not included: reason for non-inclusion, age, gender, and disease. Only one order number will be used to designate such patients in a manner so that they may be identified. Patients not included will be compared to patients included in the database of characteristics recorded in order to verify the absence of a selection bias or of inclusion bias.

Adverse events will be collected *via* the eCRF by doctors at the usual follow-up consultations, for all patients in the study. When applicable, requests for further information from the Pfizer pharmacovigilance department will be sent to the person who reported the event (participating doctor). All reports (initial and follow-up reports) will be grouped together via a centre number and patient number.

Patients' questionnaires on measurement of compliance and patients' questionnaires on measurement of quality of life will be sent to the CRO in charge of their data entry.

After validation of the database by Pfizer, paper questionnaires will undergo double data entry with the CRO's own software for patients' questionnaires in paper format. Periodic update reports on progression of data entry will be edited by the CRO and sent to Pfizer.

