### **9.7.2. Analysis of the primary objectives**

The following parameters will be evaluated in order to respond to the primary objectives:

- The percent of patients presenting with adverse events considered related to bosutinib by the participating doctor will be described overall (all grades of seriousness combined, all types of events combined), depending on grade: 1, 2, 3 and 4 and grades 3/4, and by type of event.
- The percent of patients who permanently discontinued treatment with bosutinib following an AE considered related to bosutinib by the participating doctor will be described overall.

Analysis of the primary objectives will be detailed in the statistical analysis plan.

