**Progression-free survival at 1, 2 and 3 years of patients treated with bosutinib:**

Progression-free survival will be defined as the duration between initiation of bosutinib and date of progression estimated by the participating doctor or death of patient (all causes combined) (Kaplan Meier method).

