### **11.5.2. Serious adverse events**

A SAE is any untoward medical occurrence in a patient administered a medicinal or nutritional product (including pediatric formulas) at any dose that:

:

- Causes death;
- Is life threatening;
- Requires hospitalization of the patient or prolongation of hospital stay (see below for circumstances under which it does not constitute an adverse event);
- Results in permanent or important disability or incapacity (important alteration of ability to perform acts of daily living);
- Results in a congenital anomaly or malformation.

Progression of the malignancy during the study (including signs and symptoms of disease progression) should not be reported as a serious adverse event, unless the outcome is fatal during the study or during the period of reporting adverse events. Hospitalization due to signs and symptoms of disease progression should not be reported as a serious adverse event. If the malignant condition has a fatal outcome during the study or during the period for reporting adverse events, then the event leading to death should be reported as an adverse event, and as a grade 5 serious adverse event.

An event will be defined as a medically important event based on medical and scientific judgement. A medically important event may not be immediately life-threatening and/or result in death or hospitalization. However, if it is established that the event can be life-threatening for the patient and/or require an intervention in order to prevent one of the aforementioned outcomes, the medically important event should be reported as serious.

Cases which enter into this category of medically important events are, for example, allergic bronchospasm, requiring intensive care in the emergency room of a hospital or at home, coagulation disorders, seizures which have not resulted in hospitalization, or development of medicinal product dependence or medicinal product abuse.

Furthermore, any suspicion of transmission of an infectious agent, pathogenic or not, by a Pfizer product is considered as a serious adverse event. This event can be suspected by clinical symptoms or test results indicating an infection in a patient exposed to a Pfizer product. The terms “suspicion of transmission” and “transmission” are considered as synonymous.

These cases are considered as unexpected and should be managed as serious cases by the Pfizer Pharmacovigilance Department. These cases can also be reported as a product defect, if applicable.

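### In patients already on bosutinib at consent, related adverse events between first dose and consent are not systematically captured, so the primary related-AE percentage can only be unchanged or too low

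*Protocol*

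**What the plan says.** - **Entry.** Under protocol section 9.2.1 (and the synopsis), a patient qualifies if bosutinib is started "at the end of the inclusion visit or during the one month prior to it".
- **Start of the AE period.** Section 11.3 runs the period from first dose, "or starting from the date on which the patient provided his/her informed consent if he/she has already been exposed to the study medicinal product". It adds: "Most often, the date of signature of the consent form corresponds to the date of inclusion of the patient in the study". The gap between first dose and the start of AE recording can therefore reach about one month.
- **Where AEs are collected.** In the section 9.3 table, the row "Safety in treatment with bosutinib" has the follow-up visit as its only source. Section 9.6.1.1 says AEs are collected through "the eCRF by doctors at the usual follow-up consultations, for all patients in the study".
- **Primary endpoints.** Sections 8.1 and 9.7.2 define the percentage with a related AE and the percentage permanently stopping after one. Neither has a time window. The first is given overall with all grades combined, then "depending on grade: 1, 2, 3 and 4 and grades 3/4".
- **Time origin.** In section 9.7.3, "Progression-free survival will be defined as the duration between initiation of bosutinib and date of progression" (or death). Overall survival and treatment duration also run from initiation.
- **Grade 5.** For a malignancy with fatal outcome, section 11.5.2 says "then the event leading to death should be reported as an adverse event, and as a grade 5 serious adverse event".

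**The concern.** The related-AE endpoint is worded as if it covered all time on bosutinib. For patients enrolled after starting the drug, the collection rules begin later. Such a patient is in the denominator from the outset, but a related AE that came and went before consent need not reach the numerator. The study is designed as a post-authorisation safety study and this is its first primary objective. The shortfall also depends on how many patients each centre enrols after treatment has begun, so it would blur comparisons between subgroups whose mix differs. A confidence interval does not reflect it.

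A related question concerns who can enter at all. A patient who stopped bosutinib for early toxicity and switched, or who died, before the inclusion visit is not observed, although early toxic stopping is what the second primary objective is meant to measure.

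**Working it through.** **1. Is there another route for pre-consent AEs?** I set the passages side by side.
- Sections 9.3 and 9.6.1.1 name only follow-up visits.
- Section 9.4.1.6 has FACT-leu completed at inclusion, and AEs the doctor identifies from it go into the study database. The form looks back 7 days and covers only its own items.
- An AE still ongoing after consent can be recorded at the next follow-up visit.
- No section asks for the interval from first dose to consent as such.

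What is lost is the patient whose related AEs all resolved before consent, were not revealed by the M0 questionnaire, and were not followed by any later related AE. The numerator can only lose patients and the denominator is unchanged, so the bias is zero or negative.

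**2. The plan's own precision.** Section 9.5 states a half-width of at most 10% for about 100 patients at a 50% rate by the Wald method. 1.96 x sqrt(0.5 x 0.5 / 100) = 0.098, or 9.8 points. The figure reproduces (97 patients would give 10 points).

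**3. Possible size.** Let p be the true proportion with a related AE, f the share of patients already treated at consent, and s the share of already-treated patients with a related AE whose related AEs all go unrecorded because they preceded consent. Taking p as equal in both groups, the observed proportion is p x (1 - f x s) and the shortfall is p x f x s. The protocol gives neither f nor s. I assume f = 25-100% and s = 5-20%. A true p of 80% is a further assumption, shown for contrast.

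| True p | f | s | Observed | Shortfall (points) | Half-width, n = 100 (points) |
|---|---|---|---|---|---|
| 50% | 25% | 5% | 49.4% | 0.6 | 9.8 |
| 50% | 50% | 10% | 47.5% | 2.5 | 9.8 |
| 50% | 100% | 20% | 40.0% | 10.0 | 9.8 |
| 80% | 25% | 5% | 79.0% | 1.0 | 7.8 |
| 80% | 50% | 10% | 76.0% | 4.0 | 7.8 |
| 80% | 100% | 20% | 64.0% | 16.0 | 7.8 |

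**4. Discontinuation.** For enrolled patients, section 9.3 collects permanent discontinuation at follow-up and section 9.7.3 describes its reason. Stopping after consent for an AE that began earlier is therefore not lost, and the formula in step 3 does not apply. What remains is selection. Section 9.2.2 bars a patient now on a treatment other than bosutinib, and a patient who died cannot consent. The non-inclusion registry (Annex 3.7) covers only patients who meet the criteria but decline, so it does not count either group.

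**5. Survival.** For already-treated patients, the interval from initiation to inclusion is free of death by design in overall and progression-free survival. It lasts at most about one month, against 3 years of follow-up from inclusion.

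**6. Grade 5.** Sections 8.1, 9.7.2 and 9.7.3 break down by grades 1 to 4 and 3/4. A fatal related AE stays in the all-grades percentage (change: 0 points) but has no severity row. At an assumed related fatal rate of 1%, 2% or 3%, the chance of at least one such patient in 100 is 1 - 0.99^100 = 63%, 1 - 0.98^100 = 87% or 1 - 0.97^100 = 95%. Each such patient lowers the severe category by at most 1 point per 100, and by nothing if that patient also had a related grade 3 or 4 event.

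**The case against.** The best defence is that section 11.3 governs reports to pharmacovigilance and does not define the endpoint, and that the case report form is a separate document (Annex 1) which may ask for more. The M0 FACT-leu and AEs ongoing at follow-up also give some capture. The partial capture stands and keeps the loss below a complete one. The rest does not close the gap: the protocol sets no other window for the database, and the sections that say where AEs are collected point to follow-up.

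Several stronger readings are tempting, and the documents do not support them.
- **That the endpoint is truncated at both ends, or that fatal events drop out.** Section 11.3 runs to at least 28 days after the last dose and takes related serious AEs at any later time. Fatal related AEs are in the all-grades figure. The grade 5 sentence itself concerns a fatal malignancy.
- **That discontinuation is understated by the same mechanism.** In enrolled patients it is not; the issue there is who can enrol.
- **That the pre-inclusion weeks are event-free for progression-free survival.** They are free of death, but progression before inclusion does not bar entry.
- **That the understatement is known to be large.** If 70% were already treated and 30% of those had their only related AE before consent, the shortfall would be 0.70 x 0.30 = 21 points. That needs every related AE in those patients to fall within at most a month, with none recorded in up to 36 months. Nothing in the protocol supports such inputs.

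**Conclusion.** The point holds for the first primary endpoint. As written, the plan has no systematic capture of related AEs between first dose and consent in patients enrolled after starting bosutinib, while the endpoint is worded without that limit. The direction is certain (zero or downward); the size is not derivable. Under the assumed ranges it is 0.6 to 10.0 points at a true 50%, so between negligible and about one planned half-width.

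The discontinuation endpoint is affected mainly by selection, whose size is also unknown. The effect on the survival curves is a death-free interval of at most about a month in already-treated patients, on secondary endpoints. The absent grade 5 row is an internal inconsistency in reporting and does not alter the overall percentage.

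**What to change.** (a) At inclusion, record AEs from first bosutinib dose to consent from the medical file (type, grade, causality, action taken), and count them in the related-AE endpoint. State the AE window in section 9.7.2. Do the same retrospectively for patients already enrolled where the file allows.

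(b) Report both primary endpoints separately for patients starting at the inclusion visit and patients already treated.

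(c) Optionally, add delayed entry at inclusion as a sensitivity analysis for treatment duration, progression-free and overall survival. It should not replace the main analysis, because early risk sets in the small phase cohorts could make it unstable.

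(d) Add grade 5 and grade >=3 rows in sections 8.1, 9.7.2 and 9.7.3.

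Cost: (a) is one form page covering at most about a month for a subset of patients. Section 9.3 already collects, retrospectively, the type and grade of AEs that ended earlier treatments, so the method is not new to the centres. The downside is retrospective ascertainment. Data collection began in October 2015 and this version dates from February 2019, so most of the benefit requires reopening files of enrolled patients. (b) to (d) need no new patient contact. (b) does need the first-dose and consent dates, and the former is already collected.

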### **11.4. Evaluation of causal relation**

The participating doctor must evaluate and report the causal relationship. For all adverse events, sufficient information must be obtained by the participating doctor in order to determine the causal relation of each adverse event. For AE considered as related to the study medicinal product (bosutinib), the participating doctor is required to perform follow-up up to resolution or stabilization of the event and/or of its sequelae to a level considered acceptable by the participating doctor, and that Pfizer is in agreement with this evaluation.

The evaluation of the causal relation by the participating doctor is the determination of the fact that there is a reasonable possibility that the study medicinal product (bosutinib) has caused or has contributed to an adverse event. If final determination of the causal relation is “unknown” and the participating doctor cannot determine if the study medicinal product (bosutinib) has caused the event, then the event must be reported within 24 hours.

If the participating doctor cannot determine the aetiology of the event but that he/she has determined that the study medicinal product (bosutinib) was not the cause of the event, this should be clearly mentioned in the case report forms and in the adverse event report form for non-interventional studies.

